5.3 Imputation rules

5.3.1 Study drug

No imputation of missing/partial start or study end date drug. If missing, the time of study end date will be imputed to 00:00:00.

5.3.2 AE date imputation

Rules for imputing the AE end date:

- If the AE end date month is missing, then the imputed end date should be set to the earliest of the study end date, 31DECYYYY or date of death.
- If the AE end date day is missing, then the imputed end date should be set to the earliest of the study end date, last day of the month or date of death.
- If AE year is missing or AE is ongoing, then the end date will not be imputed.

Rules for imputing the AE start date:

- If imputing end dates, then this should be done prior to calculating imputed start dates.

The following table explains the notation used in the logic matrix. Please note that **missing start dates** will not be imputed.

	Day	Month	Year
Partial Adverse Event Start Date	Not used	MON	YYYY
Treatment Start Date	Not used	TRTM	TRTY

The following matrix explains the logic behind the imputation.

	MON MISSING	MON < TRTM	MON = TRTM	MON > TRTM
YYYY MISSING	(1) No convention	(1) No convention	(1) No convention	(1) No convention
YYYY < TRTY	(2.a) Before Treatment Start	(2.b) Before Treatment Start	(2.b) Before Treatment Start	(2.b) Before Treatment Start
YYYY = TRTY	(4.a) Uncertain	(4.b) Before Treatment Start	(4.c4.c) Uncertain	(4.c) After Treatment Start
YYYY > TRTY	(3.a) After Treatment Start	(3.b) After Treatment Start	(3.b) After Treatment Start	(3.b) After Treatment Start

Before imputing AE start date, find the AE start reference date.

1. If the (imputed) AE end date is complete and the (imputed) AE end date < treatment start date, then AE start reference date = min(informed consent date, earliest visit date).
2. Otherwise, AE start reference date = treatment start date.

Impute AE start date:

1. If the AE start date year value is missing, then the date uncertainty is too high to impute a rational date. Therefore, if the AE year value is missing, then the imputed AE start date is set to NULL.
2. If the AE start date year value is less than the treatment start date year value, then the AE started before treatment. Therefore:
 - a. If AE month is missing, then the imputed AE start date is set to the mid-year point (01JulYYYY).
 - b. Otherwise, if AE month is not missing, then the imputed AE start date is set to the mid-month point (15MONYYYY).
3. If the AE start date year value is greater than the treatment start date year value, then the AE started after treatment. Therefore:
 - a. If the AE month is missing, then the imputed AE start date is set to the year start point (01JanYYYY).
 - b. Otherwise, if the AE month is not missing, then the imputed AE start date is set to the later of month start point (01MONYYYY) or AE start reference date + 1 day.
4. If the AE start date year value is equal to the treatment start date year value:
 - a. If the AE month is missing, then the imputed AE start date is set to the AE reference start date + 1 day.
 - b. If the AE month is less than the treatment start month, then the imputed AE start date is set to the mid-month point (15MONYYYY).
 - c. Otherwise, if the AE month is equal to the treatment start date month or greater than the treatment start date month, then the imputed AE start date is set to the later of (month start point (01MONYYYY), AE start reference date + 1 day).

If complete (imputed) AE end date is available and the imputed AE start date is greater than the (imputed) AE end date, then imputed AE start date should be set to the (imputed) AE end date.

5.3.3 Concomitant medication date imputation

Rules for imputing the CM end date (including on-going records):

- When the medication is ongoing at the end of the study, no numeric end date is derived.
 - If the end date is completely missing no numeric end date is derived.
- a) If CM end day is missing and CM month/year are non-missing, then impute CM date as the minimum of study end date and the last day of the month.
 - b) If CM end day/month are missing and CM year is non-missing, then impute CM date as the minimum of study end date and the end of the year (31DECYYYY).

- c) If imputed CM end date is less than the complete CM start date, use the complete CM start date as the imputed CM end date.

Rules for imputing the CM start date:

- If imputing end dates, then this should be done prior to calculating imputed start dates.

The following table explains the notation used in the logic matrix.

	Day	Month	Year
Partial CM Start Date	Not used	MON	YYYY
Treatment Start Date	Not used	TRTM	TRTY

The following matrix explains the logic behind the imputation.

	MON MISSING	MON < TRTM	MON = TRTM	MON > TRTM
YYYY MISSING	(2.a) Uncertain	(2.a) Uncertain	(2.a) Uncertain	(2.a) Uncertain
YYYY < TRTY	(2.a) Before Treatment Start	(2.b) Before Treatment Start	(2.b) Before Treatment Start	(2.b) Before Treatment Start
YYYY = TRTY	(4.a) Uncertain	(4.b) Before Treatment Start	(4.a) Uncertain	(4.c) After Treatment Start
YYYY > TRTY	(3.a) After Treatment Start	(3.b) After Treatment Start	(3.b) After Treatment Start	(3.b3.b) After Treatment Start

1. If the CM start date year value is missing, then the imputed CM start date is set to one day prior to *Treatment start date (TR01SDT)*.
2. If the CM start date year value is less than the *Treatment start date (TR01SDT)* year value, then the CM started before treatment. Therefore;
 - a) If the CM month is missing, then the imputed CM start date is set to the mid-year point (01JulYYYY).
 - b) Else if the CM month is not missing, then the imputed CM start date is set to the mid-month point (15MONYYYY).
3. If the CM start date year value is greater than the *Treatment start date (TR01SDT)* year value, the CM started after treatment. Therefore;
 - a) If the CM month is missing, then the imputed CM start date is set to the year start point (01JanYYYY).
 - b) Else if the CM month is not missing, then the imputed CM start date is set to the month start point (01MONYYYY).
4. If the CM start date year value is equal to the *Treatment start date (TR01SDT)* year value;

- a) And the CM month is missing or the CM month is equal to the *Treatment start date (TR01SDT)* month, then the imputed CM start date is set to one day prior *Treatment start date (TR01SDT)*.
- b) Else if the CM month is less than the *Treatment start date (TR01SDT)* month, then the imputed CM start date is set to the mid-month point (15MONYYYY).
- c) Else if the CM month is greater than the *Treatment start date (TR01SDT)* month, then the imputed CM start date is set to the month start point (01MONYYYY).

If complete (imputed) CM end date is available and the imputed CM start date is greater than the complete (imputed) CM end date, then imputed CM start date should be set to the complete (imputed) CM end date.

If there is no end date and ongoing check is not ticked, the CM will be considered as ongoing and included in the summary table.

5.3.3.1 Prior therapies date imputation

All therapies on the Prior urticaria therapy CRF page will be considered as prior. No additional imputation will be performed.

5.3.3.2 Post therapies date imputation

Not applicable.

5.3.3.3 Other imputations

Surgical and medical procedures date imputation

Missing data for surgical and medical procedures will be imputed following the same rule for CM date.

Medication history date imputation

Only missing medication history date for CSU diagnosis will be imputed to calculate the duration of CSU. No additional imputation will be performed for other medical history information.

Rules for imputing the MH start date:

1. If the MH start date year value is missing, the imputed MH start date is set to one day prior to *Treatment start date (TR01SDT)*;
2. If the MH start date year value is less than the *Treatment start date (TR01SDT)* year value, the MH started before treatment; Therefore:
 - a) If the MH month is missing, the imputed MH start date is set to the mid-year point (01JulYYYY).
 - b) Else if the MH month is not missing, the imputed MH start date is set to the mid-month point (15MONYYYY).
3. If the MH start date year value is equal to the *Treatment start date (TR01SDT)* year value;

- a) And the MH month is missing or the MH month is equal to the *Treatment start date (TR01SDT)* month, then the imputed MH start date is set to one day prior *Treatment start date (TR01SDT)*.
- b) Else if the MH month is less than the *Treatment start date (TR01SDT)* month, the imputed MH start date is set to the mid-month point (15MONYYYY).
- c) Else if the MH month is greater than the *Treatment start date (TR01SDT)* month, the imputed MH start date is set to the month start point (01MONYYYY).

5.4 AEs coding/grading

Not applicable.

5.5 Laboratory parameters derivations

Type Clinically notable criteria

The following notable criteria will be used in the study:

Table 5-2 Clinically notable criteria

Variable	Notable criterion	
Creatinine (umol/L), Plasma/Serum Platelets (10E9/L), Blood	>= 50% increase compared to baseline < 75 x10E9/L	
Creatinine (umol/L), Plasma/Serum	>ULN – 1.5 x ULN >1.5 - 3.0 x ULN; >1.5 - 3.0 x baseline >3.0 - 6.0 x ULN; >3.0 x baseline	
Blood urea nitrogen* (mmol/L)	1.25 – 2.5 x ULN >2.5 – 5.0 x ULN >5.0 – 10.0 x ULN >10.0 x ULN	
Albumin (g/L)	<LLN - 30 g/L <30 - 20 g/L <20 g/L	
Alanine aminotransferase, ALT (U/L)	Normal baseline >ULN - 3.0 x ULN >3.0 – 5.0 x ULN >5.0 – 20.0 x ULN >20.0 x ULN	Baseline abnormal 1.5 – 3.0 x baseline >3.0 – 5.0 x baseline >5.0 – 20.0 x baseline >20.0 x baseline
Aspartate aminotransferase, AST (U/L)	Normal baseline >ULN - 3.0 x ULN >3.0 – 5.0 x ULN >5.0 – 20.0 x ULN >20.0 x ULN	Baseline abnormal 1.5 – 3.0 x baseline >3.0 – 5.0 x baseline >5.0 – 20.0 x baseline >20.0 x baseline

Variable	Notable criterion	
Alkaline phosphatase, ALP (U/L)	Normal baseline >ULN – 2.5 x ULN >2.5 – 5.0 x ULN >5.0 – 20.0 x ULN >20.0 x ULN	Baseline abnormal 2.0 – 2.5 x baseline >2.5 – 5.0 x baseline >5.0 – 20.0 x baseline >20.0 x baseline
Gamma glutamyl transferase, GGT (U/L)	Normal baseline >ULN – 2.5 x ULN >2.5 – 5.0 x ULN >5.0 – 20.0 x ULN >20.0 x ULN	Baseline abnormal 2.0 – 2.5 x baseline >2.5 – 5.0 x baseline >5.0 – 20.0 x baseline >20.0 x baseline
Bilirubin (umol/L)	Normal baseline >ULN – 1.5 x ULN >1.5 – 3.0 x ULN >3.0 – 10.0 x ULN >10.0 x ULN	Baseline abnormal >1.0 – 1.5 x baseline >1.5 – 3.0 x baseline >3.0 – 10.0 x baseline >10.0 x baseline
Platelets (10E9/L), Blood	<LLN # to 75 x10E9/L <75 - 50 x10E9/L < 50- 25 x10E9/L < 25 x10E9/L	
Leukocytes, WBC (10E9/L)	<LLN - 3.0 x 10E9/L <3.0 - 2.0 x 10E9/L <2.0 - 1.0 x 10E9/L <1.0 x 10E3 /mL >100 x 10E9/L (leukocytosis, grade 3)	
Hemoglobin (g/L)	<LLN - 100 g/L <100 - 80g/L <80 g/L	
Lymphocytes (10E9/L)	<LLN - 0.8 x 10E9/L <0.8 - 0.5 x 10E9/L <0.5 - 0.2 x 10E9/L <0.2 x 10E9/L >4.0 - 20 x 10E9/L (grade 2 lymphocytosis) >20 x 10E9/L (grade 3 lymphocytosis)	
Neutrophils (10E9/L)	<LLN - 1.5 x 10E9/L <1.5 - 1.0 x 10E9/L <1.0 - 0.5 x 10E9/L <0.5 x 10E9/L	

# LLN = 140 x10E9/L
 
* No CTCAE grades provided for BUN. Values derived from Division of Microbiology and Infectious Diseases (DMID) grading system
 
When the parameters have different criteria for different baseline status (e.g., ATL, AST), the patients with normal baseline will follow the criteria on the left side, and the patients with abnormal baseline will follow the criteria on the right side.
		

Liver-enzyme abnormalities

Table 5-3 Liver- enzyme abnormalities

Parameter	Notable criterion
ALT	>3xULN; >5xULN; >10xULN; >20xULN

Parameter	Notable criterion
ALT or AST	>3xULN; >5xULN; >8 xULN;>10xULN; >20xULN
(ALT or AST) & TBL	>3xULN & (TBL >1.5xULN; >2xULN)
(ALT or AST) & INR	>3xULN & INR>1.5
TBL	1 xULN; 1.5xULN ; >2xULN
ALP	1.5xULN ; >2xULN; >5xULN
ALP & TBL	> 3xULN; > 5xULN; & (TBL 2xULN;)
(ALT or AST) & TBL & ALP	ALT or AST>3xULN & (TBL)>2xULN & ALP<2xULN (potential Hy's Law case)

AST = Aspartate aminotransferase; also known as SGOT, ALT = Alanine aminotransferase; also known as SGPT, ALP = Alkaline phosphatase, TBL = Total bilirubin

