2.7.3 Laboratory data

The listings for laboratory evaluations will be presented for 3 groups of laboratory tests (hematology, serum chemistry, urinalysis) in each cohort separately.

Listings for the change from baseline to each study visit and maximum/minimum value will be generated. These listings will be presented by test group, laboratory test and treatment group. Change from baseline will only be summarized for subjects with both baseline and post baseline values for quantitative parameters, and the maximum/minimum value could come from post-baseline scheduled, unscheduled or premature discontinuation visits. Data from local laboratories will be presented in the listings together. For point of care tests (POCT), the clinical sites in China will be allowed to analyze several parameters such as urine/serum for pregnancy test and urinalysis as per clinical site practice, these results will be flagged in the listings.

The numerical part of the reported result will be treated as the actual LLOQ or ULOQ. These laboratory values will be displayed in listings using the standard unit with the reported sign (“<” or “>”).

The number of participants with newly occurring or worsening abnormalities during the study will be listed by treatment based on the range of the observed data. A case is considered as a newly occurring abnormality if the value is not notable or missing at baseline but is notable thereafter during the study. A case is considered as a worsening abnormality if the value is notable at baseline and at least one post-baseline value during the study is worse than baseline.

If an adolescent subject turned to be an adult subject during the study, the normal range, notable criteria for analysis will be based on the age by the visit assessment.

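### SAP Table 5-2 prints the lowest leukocyte band per mL, so counts from 0.001 to just under 1.0 x 10E9/L meet no leukocyte notable criterion

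*SAP*

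**What the plan says.** SAP Section 5.5 introduces Table 5-2 as operative: "The following notable criteria will be used in the study". The leukocyte row is declared in 10E9/L. Its four low bands read "<LLN - 3.0 x 10E9/L <3.0 - 2.0 x 10E9/L <2.0 - 1.0 x 10E9/L <1.0 x 10E3 /mL". The first three are in the row's unit and the fourth is per mL. The row also has one high band, above 100 x 10E9/L, which plays no part here.

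Two neighbouring rows show the intended pattern. The two lowest lymphocyte bands are "<0.5 - 0.2 x 10E9/L <0.2 x 10E9/L" and the two lowest neutrophil bands are "<1.0 - 0.5 x 10E9/L <0.5 x 10E9/L". In each, the lowest band begins where the one above it ends, in the row's unit.

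SAP Section 2.7.3 uses notable status to decide what is listed as a new or worsening abnormality. On new ones it says: "A case is considered as a newly occurring abnormality if the value is not notable or missing at baseline but is notable thereafter". An abnormality counts as worsening when the baseline value is already notable and at least one later value is worse than baseline. No other place in the protocol or SAP gives a different leukocyte cut.

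**The concern.** A set of severity bands should cover every value below its upper limit. Here the unit changes between the third and fourth bands while the numeral stays at 1.0, so the printed cut drops by a factor of 1000 and leaves a hole between the bands.

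The hole lies at the severe end. If the table is programmed literally, a participant whose leukocytes go from a normal baseline to a mildly or moderately low count is flagged on the leukocyte row. One whose count goes straight to a much lower value is not. For this analyte the flag would work in the wrong direction. A baseline count inside the hole would also be treated as not notable.

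The stake is the correctness of one safety flag. No efficacy result, test or treatment decision depends on it.

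**Working it through.** **Inputs, all from SAP Table 5-2**
- Row unit: 10E9/L.
- Third low band: "<2.0 - 1.0 x 10E9/L", so its lower end is 1.0 x 10E9/L.
- Fourth low band: below 1.0 x 10E3 per mL.

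**Step 1: put the fourth cut in the row's unit.** Multiply the count per mL by 1000 mL/L, then divide by 10E9.
- 1.0 x 10E3 per mL x 1000 mL/L = 1.0 x 10E6 per L.
- 1.0 x 10E6 / 10E9 = 0.001, so the cut is 0.001 x 10E9/L.
- Ratio to the end of the third band: 1.0 / 0.001 = 1000.

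Reading 10E3 and 10E9 as strict E-notation (1e4 and 1e10) gives the same result: (1e4 x 1000) / 1e10 = 0.001.

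**Step 2: assign counts to bands, as printed and with the fourth cut at 1.0 x 10E9/L.**

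| Count (x 10E9/L) | As printed | Cut at 1.0 |
|---|---|---|
| 2.5 | second band | second band |
| 1.5 | third band | third band |
| 1.0 | third band | third band |
| 0.99 | none | fourth band |
| 0.5 | none | fourth band |
| 0.1 | none | fourth band |
| 0.01 | none | fourth band |
| 0.001 | none | fourth band |
| 0.0009 | fourth band | fourth band |

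The uncovered range is therefore 0.001 up to, but not including, 1.0 x 10E9/L.

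**Step 3: compare with the other rows that step down in bands.**

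| Row | Band above ends at | Lowest band starts below |
|---|---|---|
| Lymphocytes (10E9/L) | 0.2 | 0.2 |
| Neutrophils (10E9/L) | 0.5 | 0.5 |
| Platelets (10E9/L) | 25 | 25 |
| Albumin (g/L) | 20 | 20 |
| Hemoglobin (g/L) | 80 | 80 |
| Leukocytes (10E9/L) | 1.0 | 0.001 |

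Only the leukocyte row fails to join.

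**Step 4: apply the rule in SAP Section 2.7.3.** Take a participant with a normal baseline count.
- A fall to 1.5 x 10E9/L meets the third band and is newly occurring.
- A fall to 0.6 x 10E9/L meets no leukocyte band. It is not newly occurring on this row unless another visit lands in a covered band.
- If the baseline count was already notable, a later fall to 0.6 x 10E9/L is still caught, because the worsening rule asks only for a value worse than baseline. The defect therefore affects mainly newly occurring cases.

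**Step 5: ask whether the neutrophil row catches the same sample.** Neutrophils are part of the leukocyte count, so neutrophils cannot exceed leukocytes. If leukocytes are below 1.0 x 10E9/L, neutrophils are below 1.0 x 10E9/L and must fall in one of the two lowest neutrophil bands, which are correctly printed. Protocol Table 8-5 includes the differential in the hematology panel, so the neutrophil value should normally be available.

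**The case against.** The strongest reply is that little is lost in practice, and most of it stands.

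- **The sample is normally flagged elsewhere.** When the differential is reported, any leukocyte count below 1.0 x 10E9/L puts neutrophils in a notable band (step 5).
- **The value is still listed.** SAP Section 2.7.3 lists change from baseline at each visit and the maximum and minimum values by test, whatever the band. Under Protocol Appendix 1, the central laboratory flags values outside the normal range for investigator review, independently of Table 5-2.
- **The exposure is small.** SAP Section 1.1 reports termination with 39 participants enrolled, and Section 1.1.2 says only 3 had completed Week 12. Laboratory output is listings. Leukopenia is not among the adverse events of special interest in SAP Section 2.7.1.2, and no discontinuation criterion in Protocol Section 9.1.1 names a leukocyte count.
- **The intent is easy to guess.** The row's unit, the end of the third band and the numeral 1.0 all point to a cut at 1.0 x 10E9/L, and a programmer may have coded that. The documents do not show how it was programmed.
- **The text may have been misread from the PDF.** 1.0 x 10E3 per microlitre is exactly 1.0 x 10E9/L, so a micro sign read as m would give the printed text. This cannot be excluded, but it is not shown either: Table 5-2 writes micro as u in the creatinine and bilirubin units, and the Greek letter is rendered correctly in SAP Section 2.5.2. Even if it happened, the cell would not be in its row's unit and would still merit restating.

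A reader might infer from the table that the safety output misses the worst leukopenia cases altogether. The documents do not support that. What is lost is the flag on the leukocyte row; the participant remains detectable through the neutrophil row and the listed values. Nor is the fourth band empty: a count below 0.001 x 10E9/L still meets it.

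**Conclusion.** The cell is wrong as printed. The lowest leukocyte cut is 1000 times below the point where it should join the band above, and counts from 0.001 to just under 1.0 x 10E9/L meet no leukocyte notable criterion. Early termination does not retire the table. The SAP drops efficacy testing but keeps the laboratory listings and the newly occurring rule that depends on these cut-offs.

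The consequence is limited to a missing newly occurring flag on one row, in a trial with 39 participants enrolled, for a finding that should be rare. This rests on two assumptions: that the printed unit is what the SAP contains, and that the table is applied literally. The view that the same sample would normally be flagged elsewhere also assumes that the differential was reported. The correction is worth making because it is a safety threshold and costs almost nothing; the impact on what the trial reports is small.

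**What to change.** In SAP Table 5-2, restate the fourth low leukocyte band as <1.0 x 10E9/L. It then continues from the third band in the row's own unit, and the four low bands join without a gap. Check the programming specification for the leukocyte criterion against the restated cell. If it was coded from the per-mL text, correct it and regenerate the listing of newly occurring and worsening leukocyte abnormalities.

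The cost is one table cell and one check of the specification. No new data or clinical judgement is needed, and no treatment or stopping rule changes.

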5.6 Statistical models

Not applicable

